8 DEMOGRAPHIC AND OTHER BASELINE CHARACTERISTICS

Demographics and baseline characteristics will be summarized with descriptive statistics using the ITT and safety population. The list of demographics and baseline characteristics to be summarized will include:

- Age (years)
- Sex at birth
- Ethnicity
- Race*
- Baseline Height (cm)
- Baseline Weight (kg)
- Baseline Body Mass Index (BMI) percentile
- Fitzpatrick Skin Type
- Prior failure of Topical Corticosteroids, Topical Calcineurin Inhibitors, Eucrisa
- Atopic Dermatitis involvement on the face, on the eyelids

 Innovaderm Research ■■■	STATISTICAL ANALYSIS PLAN, Version 1.0
Protocol Number: ARQ-151-315	Sponsor: Arcutis Biotherapeutics, Inc.

- Number of AD flares in the last 12 months
- Number of prior prescription treatments ever used
- Duration of disease (months)
- Baseline vIGA-AD
- Average weekly baseline WI-NRS
- Daily baseline WI-NRS
- Baseline BSA (%)
- Baseline BSA (%) Group - <10% and ≥10%, tertile groups
- Baseline EASI total score
- Baseline EASI score group - ≤7 and >7, tertile groups
- Baseline SCORAD
- Baseline CDLQI (≥ 4 years of age)
- Baseline IDQoL (< 4 years of age)
- Baseline DFI
- Baseline POEM

*Subjects who reported more than one race will be summarized as 'Multiple' races in the table. All races selected will be displayed in the listing.

BMI (kg/m²) = (weight in kg)/ [(height in cm/100)²]. Baseline height will be used to derive BMI for all post-baseline visits until height is collected again (planned at week 4). After BMI is calculated using the same formula above for children, it is expressed as a percentile obtained from either a graph or a percentile calculator. Percentiles will be calculated using data files and instructions provided by the CDC (https://www.cdc.gov/growthcharts/percentile_data_files.htm).

A listing of all demographics, analysis population flag, reason not included in the efficacy analysis will be provided.

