2. SCHEDULE OF VISITS AND ASSESSMENTS

Study Procedure	Screen	Baseline Day 1	Week 1 Day 8	Week 2 Day 15	Week 4 Day 29/ET
Visit	1	2	3	4	5
Visit Window	-30 days	N/A	± 3 days	± 3 days	± 3 days
Parents/Caregivers informed consent	X				
Demographics	X				
Medical and surgical history	X				
Physical examination ^a	X	X			X
I/E criteria	X	X			
Hematology and Serum Chemistries ^b	X				
Vital signs, weight, height ^c	X	X	X	X	X
vIGA-AD ^d , EASI ^d , BSA ^d , SCORAD ^d	X	X	X	X	X
WI-NRS pruritus ^e	X	X	X	X	X
POEM ^f	X	X	X	X	X
Local Tolerability Assessments ^g		X	X	X	X
CDLQI ^h , IDQoL ^h , DFI ^h	X	X	X	X	X
Medical Photography ⁱ		X	X		X
Drug application and Parents/Caregivers training in clinic ^j		X	X	X	
Dispense/Redisperse investigational product kit ^k		X	X	X	X ^l
Weigh investigational product tubes ^l		X	X	X	X
Dispense/review diary	X	X	X	X	X
Compliance determination ^m			X	X	X
Adverse event assessment ⁿ	X	X	X	X	X
Concomitant medications	X	X	X	X	X
Study Exit ^o					X

- a. Limited physical examination: skin (including assessment of Fitzpatrick skin type at Screening only), lungs, and heart only.
- b. To be collected at Screening. In addition, laboratory safety tests may be performed at various unscheduled time points, if deemed necessary by the Investigator.
- c. Height will be collected at Screening and Week 4/Day 29. Weight should be obtained using a calibrated weight scale and the same scale should be used for a subject throughout the duration of the study. The subject should remove shoes and heavy clothing (sweaters or jackets), and empty pockets. The subject should stand with both feet in the center of the scale with their arms at their side and hold still. Record the weight to the nearest decimal fraction (for example, 25.1 kilograms). Measure the weight in triplicate and report the average weight in EDC. A 5% weight loss (whether or not intentional or other explained) should be reported to the medical monitor in a timely manner and before the next clinic visit.

Footnotes from above table:

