- d. The vIGA-AD assessment will be a 5-point scale ranging from clear (0) to severe (4) and is evaluated for the entire body except the scalp, palms, and soles. EASI takes into account overall severity of erythema, infiltration/papulation, excoriation, and lichenification, in addition to extent of BSA affected. The 4 clinical signs will be graded on a 4-point scale (0 [absent] to 3 [severe]) for 4 body regions (head and neck, upper extremities, lower extremities, and trunk). Total EASI score will be calculated as a sum of scores of all 4 body regions. EASI total score will range from 0 (absent) to 72 (severe). Total BSA affected by AD will be determined for all body surfaces except the scalp, palms and soles. **The vIGA-AD assessment should be completed prior to other physician assessments.** SCORAD total score will range between 0 and 103.
- e. Parents/guardians/caregivers of children will report pruritus at home on a daily basis starting 7 days prior to the Baseline/Day 1 visit, and then every day thereafter using a diary. WI-NRS score will be determined by assessing worst itch over the past 24 hours. The scale is from 0 (no itch) to 10 (worst itch) and this value will be recorded each day. Caregiver/parents will be given instructions on how to complete this questionnaire.
- f. POEM will be completed for all subjects by proxy completion.
- g. Local tolerability assessments should be recorded prior to study drug application for the Investigator assessment of skin irritation (Berger and Bowman skin irritation score) and 10-15 minutes post-drug application for the Subject's '0-3' burning/stinging assessment. Parents/guardians will complete assessment for subjects. Subject's burning/stinging assessment at Week 4/Day 29 will be provided by a recall assessment of burning/stinging experienced post drug application on the previous day (Day 28). **Note for Investigator tolerability assessments: reactions at the site of product application, which may occur post-Baseline, should be differentiated from the preexisting inflammation associated with the subject's atopic dermatitis.** If a subject is entering ARQ-151-313 Open Label Extension study, then the Subject's '0-3' burning/stinging assessment will be performed as described in the ARQ-151-313 protocol for Baseline/Day 1.

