4.4.6. Oral Roflumilast Tablet

Oral roflumilast (DALIRESP®) has been approved globally for the treatment of COPD and has been evaluated in nine phase III/IV randomized double-blind clinical trials ([Wedzicha 2016](#)). Overall, the safety of oral roflumilast has been well established in its targeted population of mostly middle- and upper-aged individuals who currently smoke cigarettes or have smoked them extensively in the past. Adverse events (AEs) reported with roflumilast tablets have been consistent with those expected for oral PDE-4 inhibitors. In a pooled analysis of safety data from 6-month and 1-year clinical trials (N=8630), the most common AEs were diarrhea, weight loss and nausea. Other AEs reported more frequently with roflumilast treatment than with placebo were back pain, influenza, insomnia and decreased appetite ([Michalski 2012](#), [Wedzicha 2016](#)).

In addition to the self-reported cases of weight loss in the 6-month and 1-year oral trials, clinically significant weight loss was also reported in two prospective studies that evaluated weight ([Michalski 2012](#)).

Psychiatric-related AEs were also greater in patients treated with roflumilast tablets (5.9%) compared to those treated with placebo (3.3%). The most common psychiatric-related AEs were insomnia, depression and anxiety. A small number of cases of completed suicide and suicide ideation have been reported in patients taking oral roflumilast in clinical trials and also during post-marketing experience ([Michalski 2012](#)).

The only contraindication to oral roflumilast is use in patients with moderate to severe liver impairment (Child-Pugh B or C), where systemic levels of roflumilast may become elevated.

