3 STUDY DESIGN

3.1 Overall Design

This is a Phase 3, parallel group, double blind, vehicle-controlled study in which ARQ-151 cream 0.05% or vehicle is applied QD x 4 weeks to subjects with mild to moderate atopic dermatitis.

At entry, subjects will have $\geq 3\%$ BSA involvement (excluding the scalp, palms, soles) and mild or moderate atopic dermatitis based on vIGA-AD assessment.

 Innovaderm Research ■■■	STATISTICAL ANALYSIS PLAN, Version 1.0
Protocol Number: ARQ-151-315	Sponsor: Arcutis Biotherapeutics, Inc.

Upon determination of eligibility, subjects will be randomized 2:1 to either ARQ-151 cream 0.05% or matching vehicle cream. The randomization will be stratified by vIGA-AD score at baseline ('Mild' vs. 'Moderate'), and by study site.

Caregivers will apply ARQ-151 cream 0.05% or vehicle cream QD to all AD affected areas and any newly appearing AD lesions that arise during the study, except on the scalp. Caregivers should maintain treatment of these areas with study drug for the duration of the study regardless of whether treatable areas of AD clear prior to Week 4/Day 29.

[figure not shown]
Subject participation involves a minimum of 5 clinic visits including Screening, Baseline/Day 1, Week 1/Day 8, Week 2/Day 15, and Week 4/Day 29. The interval between the Screening and Baseline/Day 1 visits could be up to 30 days, therefore the anticipated maximum duration of subject participation is approximately 8 weeks.

At the Week 4/Day 29 visit, subjects may be eligible to enroll in a 12-month, open label extension study (ARQ-151-313) evaluating ARQ-151 cream 0.15% QD and 0.05% QD. All subjects will have the option to enroll into the ARQ-151-313.

The trial design is represented schematically in [Figure 1](#).

	STATISTICAL ANALYSIS PLAN, Version 1.0
Protocol Number: ARQ-151-315	Sponsor: Arcutis Biotherapeutics, Inc.

Figure 1 Study Schema

 Innovaderm Research ■■■	STATISTICAL ANALYSIS PLAN, Version 1.0
Protocol Number: ARQ-151-315	Sponsor: Arcutis Biotherapeutics, Inc.

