5.2 Baseline

Unless otherwise specified, baseline value will be defined as the last non-missing assessment prior to or concurrently with the first study treatment application (including unscheduled/retest assessments). The randomization date will be used in place of the date of first treatment application for randomized subjects who discontinue without having treatment applied. If the last non-missing assessment is performed on the same date as the first study treatment administration and time is not available, it is assumed that the assessment took place prior to IP application, per study site training, and the assessment will be considered as baseline, except for adverse events (AEs) and medications starting on the first study treatment dose administration date which will be considered postbaseline.

Average weekly baseline WI-NRS is defined as the average of all non-missing scores reported during the last 7 days prior to treatment if at least 4 of 7 evaluable daily WI-NRS questionnaires available. Daily baseline WI-NRS is defined as the last non-missing assessment prior to or concurrently with the first study treatment dosing. Day 1 WI-NRS score will be used to calculate the value for week 1 only when it is collected after the application of the first study drug. If Day 1 WI-NRS score is collected prior to or concurrently with the application of the first study drug, then the Day 1 WI-NRS score will be included in baseline calculation.

For investigator/subject tolerability assessments, baseline is derived as the measurement taken on the day of first application of study drug.

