13.3 Vital Signs

Descriptive statistics will be presented for vital signs (systolic blood pressure, diastolic blood pressure, heart rate, body temperature, and weight). Observed values, change from baseline and percent change from baseline values will be presented by treatment group at each scheduled visit.

The number and percentage of subjects with gain or lose $\geq 5\%$ from baseline in body weight over the course of the study will be summarized. The BMI percentile rather than BMI kg/m^2 will be summarized using descriptive statistics (n, mean, standard deviation, median, Q1, Q3, minimum, and maximum) on observed values, change from baseline and percent change from baseline values.

A listing of all vital sign assessments including weight, BMI, and BMI percentile will be provided.

 Innovaderm Research ■■■	STATISTICAL ANALYSIS PLAN, Version 1.0
Protocol Number: ARQ-151-315	Sponsor: Arcutis Biotherapeutics, Inc.

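### BMI percentile at baseline, Week 1 and Week 2 rests on a Screening height up to 30 days older than Day 1, which on average pulls the within-arm Week 4 change downward; percent change of a percentile is not interpretable

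*SAP*

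**What the plan says.** - **When height is taken.** Protocol section 2, footnote c: "Height will be collected at Screening and Week 4/Day 29". Weight is scheduled at every visit, Screening and Day 1 included.
- **How old the Screening height can be.** SAP 3.1: "The interval between the Screening and Baseline/Day 1 visits could be up to 30 days".
- **What baseline means.** SAP 5.2: "baseline value will be defined as the last non-missing assessment prior to or concurrently with the first study treatment application". Applied to each component, this gives the Day 1 weight and the Screening height. The SAP does not spell out that pairing for baseline BMI; it follows from the rule.
- **Which height enters later BMI values.** SAP 8: "Baseline height will be used to derive BMI for all post-baseline visits until height is collected again (planned at week 4". Weeks 1 and 2 keep the Screening height and Week 4 takes the new one.
- **How the percentile is obtained.** SAP 8: "Percentiles will be calculated using data files and instructions provided by the CDC". The age to be used at each visit is not stated.
- **What is reported.** SAP 13.3 summarises the BMI percentile, in place of BMI in kg/m², "on observed values, change from baseline and percent change from baseline values".

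SAP 13.3 also summarises weight itself and the number of children gaining or losing at least 5% of body weight. SAP 13 rules out formal inference on safety data.

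**The concern.** Two separate things look wrong.

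First, the heights and weights inside BMI belong to different dates at every visit from Day 1 to Week 2, and to the same date at Week 4. Children of this age grow taller, so an old height is on average too short and the BMI built on it too high. The Week 4 change then sets about 28 days of weight gain against 28 days of height growth plus the whole screening gap, up to about 58 days. A child whose true BMI percentile is constant would on average appear to fall.

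Second, a percentile is a bounded, non-linear transform of BMI. Dividing its change by its starting value makes the same physical shift look large in a lean child and negligible in a heavy one.

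What is at stake is how a descriptive safety table is read. For the oral tablet, Protocol 4.4.6 notes that "clinically significant weight loss was also reported in two prospective studies that evaluated weight". Readers will therefore look at body-size tables, and a within-arm fall in BMI percentile at Week 4 could be taken as a signal, or a real fall dismissed as artefact.

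**Working it through.** The documents give no growth rate, BMI spread or expected error, so there is no stated figure to reproduce.

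**Inputs from the documents.** The Screening-to-Day 1 gap is at most 30 days (SAP 3.1). A practical minimum of about 7 days is an inference: Protocol section 2, footnote e says "Parents/guardians/caregivers of children will report pruritus at home on a daily basis starting 7 days prior to the Baseline/Day 1 visit", and Protocol 7.2.3 has caregivers trained for this at Screening.

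**Assumptions, not in the documents.** Central case: growth 7 cm/year, Screening height 100 cm, BMI coefficient of variation (CV) 8%, true BMI percentile constant. Range: 5–9 cm/year, 88–112 cm, CV 7–10%. Percentile points use a normal approximation on log BMI, because the CDC tables were not available.

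**Step 1: overstatement of baseline BMI.** The recorded value divides by the squared Screening height instead of the squared Day 1 height:

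overstatement = (H_Day1 / H_Screening)² − 1, with H_Day1 = 100 + 7 × gap / 365.25

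**Step 2: false change at Week 4 for a child truly at the 50th percentile.** Week 4 BMI is correct, so

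false change = 50 − 100 × Φ( ln(1 + overstatement) / 0.08 )

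| Gap (days) | Growth over gap (cm) | Baseline BMI overstated by | False Week 4 change (points) |
|---|---|---|---|
| 0 | 0 | 0 | 0 |
| 7 | 0.13 | 0.27% | −1.3 |
| 14 | 0.27 | 0.54% | −2.7 |
| 30 | 0.57 | 1.15% | −5.7 |

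For the 30-day row: 1.00575² − 1 = 1.15%; ln(1.0115) / 0.08 = 0.143; Φ(0.143) = 0.557; 50 − 55.7 = −5.7.

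Over the full assumed range at 30 days, the overstatement is 0.7% to 1.7% and the false fall 2.9 to 9.4 points.

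**Step 3: Weeks 1 and 2.** The height stays frozen while the child grows. With a 30-day gap the overstatement becomes 1.42% at Week 1 (37 days of growth) and 1.69% at Week 2 (44 days). Against baseline that is a false rise of 1.42 − 1.15 = 0.27% and 1.69 − 1.15 = 0.54% of BMI, before the drop at Week 4.

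**Step 4: individual children.** A simulation of the central growth case with an assumed 1% weight noise and height error of 0.3–0.5 cm gives the share of children whose BMI falls by Week 4 when true BMI is constant: 50% at no gap, 55–56% at 7 days, 72–76% at 30 days.

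**Step 5: percent change of a percentile.** No growth assumption is needed. Lower z by 0.1:

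| Start | z before → after | Percentile after | Percent change |
|---|---|---|---|
| 5th | −1.645 → −1.745 | 4.0 | −19% |
| 50th | 0 → −0.1 | 46.0 | −8% |
| 95th | 1.645 → 1.545 | 93.9 | −1.2% |

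**The case against.** The strongest reply is that no conclusion of the trial depends on this table, and most of that reply stands.

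- Randomisation spreads screening gaps and growth over both arms, so the drug-versus-vehicle contrast is not biased in expectation.
- BMI percentile is not among the safety endpoints in SAP section 2; weight gain or loss of at least 5% is. That measure and the weight summaries in SAP 13.3 do not use height. A reader might infer that the plan's monitoring of weight loss is compromised; it is not.
- A reader might also infer that every normally growing child will show a false fall. The documents do not support that. Thirty days is a maximum, no typical gap is given, the effect vanishes at a gap of zero, and at 14 days the growth (0.27 cm) is below the assumed height error of 0.3–0.5 cm.
- The early rise should not be blamed on the change of height. No change occurs at Weeks 1 and 2; the rise comes from the frozen height.
- The weight-loss background concerns oral tablets in COPD, and Protocol 4.5.2 says the topical profile so far looks different.
- SAP 13.3 also reports median and quartiles, which resist a few extreme percent changes. The mean and SD do not.

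What the reply does not remove is a systematic direction in the within-arm change, and a percent-change column whose values cannot be compared between children.

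**Conclusion.** The point holds as a minor one about a descriptive safety summary. The stale Screening height, its use through Week 2 and its replacement at Week 4 follow from the SAP's own rules. The Week 4 value is correctly built; the error sits in the baseline, Week 1 and Week 2 values, and so in change from baseline. It is an average tendency proportional to the screening gap, and its size depends on growth and BMI-spread figures from outside the documents. The direction depends only on children growing taller between Screening and Day 1.

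The objection to percent change of a percentile rests on no growth assumption and is the firmer half of the point.

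**What to change.** In SAP 13.3:

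1. Drop percent change of BMI percentile.
2. Beside the percentile, summarise observed value and change in BMI-for-age z-score, and state that age at each visit is used.
3. Either base BMI change on Screening and Week 4, the two scheduled visits where height and weight are taken together, or footnote the Day 1, Week 1 and Week 2 values as using the Screening height.

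Height interpolated between the two measurements would remove the Week 4 artefact if growth is linear, but should be a supplementary calculation only. It puts a post-treatment height into a baseline value, and it defines baseline differently for children with no second height.

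The cost is a few lines of SAP text and some programming, with no new measurements. The drawback of the Screening-to-Week 4 change is that it includes the pre-treatment screening interval, which the table should say.

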9 SURGICAL AND MEDICAL HISTORY

Surgical and medical history will be coded according to the Medical Dictionary for Regulatory Activities (MedDRA), Version 25.0 or later.

 Innovaderm Research ■■■	STATISTICAL ANALYSIS PLAN, Version 1.0
Protocol Number: ARQ-151-315	Sponsor: Arcutis Biotherapeutics, Inc.

Surgical and medical history will be summarized by system organ class (SOC) and preferred term (PT) using the safety analysis set. A subject who experienced the same surgical and medical history event multiple times will be counted only once for the corresponding PT. Similarly, if a subject experienced multiple surgical and medical history events within the same SOC, the subject will be counted only once for that SOC. Surgical and medical history events will be sorted alphabetically by SOC and within each SOC the PT will be presented by descending frequency in the safety analysis set.

10 PRIOR AND CONCOMITANT MEDICATIONS

Medications will be coded according to the World Health Organization Drug Dictionary (WHO-DD) B3 March 2022 or later.

Prior medications are defined as any medication started and discontinued prior to the first study treatment dosing. Concomitant medications are defined as any medication taken after the first study treatment dosing, including those who started prior to the first study treatment date and continued past that date. See [Appendix 2](#) for handling of completely or partially missing dates for prior and concomitant medications.

Incidence of prior and concomitant medications will be tabulated by ATC level 3 and PT using the safety analysis set. A subject with the same medication taken multiple times will be counted only once for the corresponding PT. Similarly, if a subject has taken more than one medication within the same ATC level, then the subject will be counted only once for that ATC. Prior and concomitant medications will be sorted alphabetically by ATC level and within each ATC level, the PT will be presented by descending order.

11 STUDY TREATMENT EXPOSURE AND TREATMENT COMPLIANCE

A summary of exposure related to Roflumilast cream and the vehicle will be presented using the safety population by treatment group. It will include descriptive statistics on the number of days on IP, as well as the number of investigational product applications based on diary, for each treatment group. The number of days on IP, will be calculated as follows:

$$[(\text{last treatment date} - \text{first treatment date}) + 1].$$

For each subject, investigational product application compliance (%) will be calculated as follows:

 Innovaderm Research ■■■	STATISTICAL ANALYSIS PLAN, Version 1.0
Protocol Number: ARQ-151-315	Sponsor: Arcutis Biotherapeutics, Inc.

$$\frac{\text{Number of investigational product applications}}{\text{Number of expected investigational product applications}} \times 100$$

Number of investigational product applications will be calculated as number of expected investigational product applications minus number of doses missed. Number of doses missed and the date that the dose was missed were collected in eCRF.

Number of expected investigational product applications will be calculated as last treatment/interruption date – first treatment date + 1. If latest treatment date \geq latest interruption date, then the latest treatment date will be used; otherwise, latest interruption date will be used in deriving the expected number of IP applications.

Descriptive statistics for the compliance as well as the number of missed applications, subjects with < 80%, [80% - 100%], and >100% compliance will be presented by treatment. Furthermore, the incidence of subjects who missed more than 3 consecutive doses and compliant subjects will be presented by treatment.

A subject will be considered compliant with the dosing regimen if the subject meets both of the following requirements:

- applies at least 80% of the expected applications during the study drug application period
- does not miss more than 3 consecutive doses

Total weight of study medication applied (determined by weighing the study medication before and after use) will be summarized by treatment using descriptive statistics. Weight of study medication used will be documented in source documents and in eCRF. Total weight of IP used is determined by subtracting minimum of (returned, remained) tube weight from the maximum of (dispensed, prepared) tube weight for each tube that was dispensed and summing the weights. Calculate Actual IP Used: maximum of (dispensed, prepared) tube weight minus minimum of (returned, remained) tube weight = ____ grams

If a tube is not returned at the end of the study or a tube weight is missing, actual IP used for the tube and total weight of IP applied during study will be missing.

Number of days on IP and compliance, including compliance collected at each clinic visit, will be displayed in a listing of study treatment administration by subject, for each treatment. A listing of drug accountability including the kit number, tube number, dispensed and returned weight will also be provided.

 Innovaderm Research ■■■	STATISTICAL ANALYSIS PLAN, Version 1.0
Protocol Number: ARQ-151-315	Sponsor: Arcutis Biotherapeutics, Inc.

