7.8. Treatment Stopping Rules

If a subject has non-cutaneous adverse events of concern, clinically significant laboratory values or any condition that the investigator determines could possibly be related to the study drug, the Investigator should immediately contact the Medical Monitor to discuss if the subject should be discontinued from treatment with investigational product.

Treatment for any individual subject will be discontinued if the subject experiences:

- A serious adverse event (SAE) or a clinically significant non-serious AE which in the opinion of the Principal Investigator or Medical Monitor warrants discontinuation from the study for that subject's well-being.
- A treatment-emergent severe (Grade 3) laboratory abnormality (confirmed by repeat sample; see [Appendix 8](#) and the Laboratory Toxicity Grading section in the appendix for more information).

Parents/caregivers will be advised to promptly report any changes in behavior that could signal psychological distress or emotional distress.

Treatment should be interrupted:

- If a subject develops an application site reaction with the clinical appearance of an 'irritation reaction', and with a severity of a Dermal Response Score of 5 (erythema, edema and papules) or greater on the scale of Berger and Bowman, treatment should be interrupted for up to one week and may then be resumed if the reaction has, in the opinion of the Investigator, adequately resolved.

Treatment should be discontinued:

- If the application site reaction reoccurs, treatment should be discontinued permanently, and the subject followed until the reaction resolves.

For cases of suspected allergic contact dermatitis, the medical monitor and sponsor should be notified and there should be discussion about performing patch testing to further evaluate. Patch testing is encouraged in such cases.

In the event of a medical emergency where unblinding is required to provide medical care to the subject, refer to the most current IWRS User Manual ([Section 6.5](#)). Contact the Medical Monitor and the Sponsor promptly.

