3.3 Treatment

Roflumilast cream 0.05% or vehicle cream will be administered QD for 28 days (+/- 3 days).

- Roflumilast cream 0.05%
- Vehicle cream

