4.2 Per Protocol (PP) Population

Per protocol population will include all subjects who are randomized, at least 80% compliant with study medication application have a vIGA-AD assessment within the Week 4 visit window, and show no “major deviations” from the study protocol that would affect the interpretation of efficacy. A complete list of major deviations from the study protocol will be created prior to unblinding and include a list of all subjects who will be excluded due to those major deviations. See section [7.2](#) for more details.

All subjects will be analyzed according to the actual treatment group they received and the randomized stratum. Actual and randomized treatment will only differ if the subject received the wrong treatment throughout their participation in the study.

4.3 vIGA-AD Moderate ITT Population

vIGA-AD Moderate ITT population will be a subset of the ITT population with vIGA-AD score (randomized score) ‘Moderate’ at randomization.

All subjects will be analyzed according to the treatment group and the stratum to which they were randomized.

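### SAP 11 ends the expected-application count at the child's last treatment date or an undefined interruption date, so an early stopper who stays to Week 4 can meet the per-protocol 80% criterion if nothing is recorded after the stop

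*SAP*

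**What the plan says.** SAP 11 gives the denominator as "Number of expected investigational product applications will be calculated as last treatment/interruption date" minus the first treatment date plus one. The later of the two end dates applies: the latest treatment date is used if it is on or after the latest interruption date; "otherwise, latest interruption date will be used in deriving the expected number of IP applications". The numerator is derived, not counted: "Number of investigational product applications will be calculated as number of expected investigational product applications minus number of doses missed". On the source of the misses: "Number of doses missed and the date that the dose was missed were collected in eCRF".

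SAP 3.3 sets the planned course: "Roflumilast cream 0.05% or vehicle cream will be administered QD for 28 days", with a tolerance of three days either way. Footnote j of the visit schedule excludes an application at the Day 29 visit, so the last planned application is on Day 28.

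The PP population (SAP 4.2, Protocol 8.1.2) requires children to be "at least 80% compliant with study medication application have a vIGA-AD assessment within the Week 4 visit window", with no major deviation affecting efficacy. Protocol 8.1.4 divides applications by the expected number but does not say how that number is fixed for a child who stops early. Both schedules of visits refer compliance determination to an IP Handling Manual.

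Protocol 6.7.1 (stopping treatment) and 6.7.2 (leaving the study) are separate lists. Protocol 6.5 has treatment stopped after disclosure to the investigator, with follow-up continuing. SAP 13.1 tabulates the two kinds of discontinuation separately.

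**The concern.** A compliance percentage used to select a PP population should show how much of the planned treatment the child received. Here the denominator shrinks with the child's own treatment period. A child who stops for good in week 1 or 2 and attends Week 4 may look fully compliant.

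The undefined interruption date does not reliably close the gap. Protocol 7.8 uses the word for a pause, where "treatment should be interrupted for up to one week and may then be resumed", and uses different language for a permanent stop: "If the application site reaction reoccurs, treatment should be discontinued permanently, and the subject followed until the reaction resolves". A permanent stop therefore need not generate an interruption date. Nor does either document say which day of an interruption the date denotes.

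At stake are the meaning of the 80% threshold in the supplemental observed-data PP analysis of the primary endpoint, and the reported compliance figures.

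**Working it through.** The plan states no figure that could be reproduced here; the check applies its formula.

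**Inputs.** Planned applications N = 28 (SAP 3.3; no application on Day 29). Last application on Day L, with no earlier misses. PP threshold 80% (SAP 4.2).

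**Formula (SAP 11).** Compliance = (expected - missed) / expected, where expected = later of last treatment date and last interruption date - first treatment date + 1.

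**Four ways the record could look after a permanent stop on Day L:**

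- A. Nothing recorded: expected = L, missed = 0, score = L/L = 100%.
- B. Only the first post-stop day recorded, as one interruption date and one missed dose: score = L/(L+1).
- C. All days to Day 28 logged as missed, denominator still ending at the last dose: expected = L, missed = 28 - L, score = (2L - 28)/L.
- D. All days logged as missed and the denominator carried to Day 28: score = L/28, the share of the course.

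| L | D (true share) | A | B | C |
|---|---|---|---|---|
| 4 | 14.3% | 100% | 80.0% | -500% |
| 7 | 25.0% | 100% | 87.5% | -200% |
| 10 | 35.7% | 100% | 90.9% | -80% |
| 14 | 50.0% | 100% | 93.3% | 0% |
| 22 | 78.6% | 100% | 95.7% | 72.7% |
| 23 | 82.1% | 100% | 95.8% | 78.3% |

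**Reading the table.**

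- The true share is below 80% for L = 1 (1/28 = 3.6%) to L = 22 (22/28 = 78.6%). At least 23 of 28 applications are needed.
- Under A, all of Days 1-22 wrongly pass. Under B, Days 4-22 wrongly pass (4/5 = 80.0%; Day 3 gives 3/4 = 75.0%).
- Under C, Days 1-22 fail as they should, but with meaningless values, and a Day 23 stop wrongly fails: (46 - 28)/23 = 78.3% against 82.1%.
- Only D is right. It needs both the missed-dose log and the denominator to run to the planned end, and neither document requires that.

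Earlier misses do not change the pattern. A Day 14 stop with two earlier misses scores 12/14 = 85.7% under A, against 12/28 = 42.9% of the course.

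**Other rules that might catch these children.**

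- *Removal for interrupting more than 50% of doses (Protocol 6.7.2).* It is discretionary, and (28 - L)/28 > 50% holds only for L = 1-13 (Day 13: 15/28 = 53.6%). Days 14-22 are out of its reach.
- *No more than three consecutive missed doses (Protocol 6.10.4, SAP 11).* This uses the same missed-dose log, and the PP definition names only the 80% part, so it is a partial safeguard.
- *Major deviations (SAP 4.2).* The list is to be made before unblinding; its contents are not given.
- *Adverse event or lack of efficacy.* SAP 5.5 sets children to missing in observed-case analyses, but is worded for discontinuing from the study. SAP 12.1.1 gives treatment discontinuation as its example, SAP 6.2.3 refers to discontinuation of treatment, and Protocol 8.2.1 does not specify study or treatment. On the broader reading, these treatment stoppers drop out of the PP result. Children who stop by parent decision or after unblinding are not covered on either reading.

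**Pauses.** A seven-day pause followed by full dosing to Day 28 gives (28 - 7)/28 = 75.0% if the pause days count as expected and missed. So their treatment can also decide PP membership, and SAP 11 does not state it.

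**The case against.** The strongest reply is that the wrong pass needs missed doses to go unrecorded. The caregiver diary is daily and includes missed doses (Protocol 6.10.4), and the eCRF holds their dates. The interruption date matters only when it is later than the last treatment date, that is, when no dose followed, so it may have been meant for unresumed stops. Protocol 6.7.2 also uses the verb interrupt for extensive non-application, not only for a short pause. The IP Handling Manual may settle the matter. And compliance over the application period can reasonably mean adherence while on treatment.

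Much of this stands, and it makes the point conditional. If post-stop days are fully logged and extend the denominator, there is no error. But logging alone is not enough, as case C shows, and SAP 11 states its own formula without supplying the missing rule. If on-treatment adherence is intended, the PP criterion does not mean 80% of the course, and the SAP should say so.

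The adverse-event and lack-of-efficacy wording also narrows the concern: the children at risk are mainly those who stop for other reasons.

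A reader might infer that early stoppers will generally enter the PP population, or that the trial's main result is inflated. The documents do not support either. A Week 4 vIGA-AD and the absence of major deviations are also required, and the primary analysis uses the ITT population. Nothing in the documents gives the number of such children or a direction of bias. Short exposure would also be visible, because SAP 11 summarises and lists days on treatment.

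**Conclusion.** The point holds in conditional form and is minor. SAP 11 ends the denominator at a date specific to the child and leaves post-stop days undefined. Depending on what is recorded, a last dose on Days 1-22 can score 100% for 3.6%-78.6% of the planned course, or the score can be too low, even negative.

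This assumes a 28-application course, no earlier misses, a permanent stop, and a child who stays for the Week 4 assessment. Stops on Days 23-27 reach 82.1%-96.4% of 28 and are not counted as errors.

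The effect is confined to the supplemental PP analysis of the primary endpoint and the compliance tables.

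**What to change.** For the PP 80% criterion and the compliance table:

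- Count expected applications from the first application through planned Day 28, or through the day before the scheduled Week 4 visit if that is earlier. For visits on Days 26, 27, 28, and 29 or later, expected is 25, 26, 27 and 28, and 20, 21, 22 and 23 applications are needed.
- Do not let an early termination visit shorten the interval. With a last dose on Day 18 and such a visit on Day 23, the score is 18/28 = 64.3%, not 18/22 = 81.8%.
- Count missed doses within the same interval, and count every day after a permanent stop as missed.
- Define interruption date, and state how days of a protocol-directed pause are counted.
- Reconcile the wording on adverse-event and lack-of-efficacy discontinuation in SAP 5.5, 6.2.3 and 12.1.1 and Protocol 8.2.1, so that it is clear whether stopping treatment or leaving the study triggers the rule.
- If on-treatment adherence is wanted, report it as a separate, labelled figure.

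The Day 28 cap keeps a child with 28 doses and a Day 37 visit at 28/28 = 100% rather than 28/36 = 77.8%. It is a convention: with a Day 32 visit and 31 possible applications, a Day 23 stop passes at 23/28 = 82.1% although it is 23/31 = 74.2% of the longer period.

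The tabulated category above 100% cannot occur, since applications are expected minus missed; removing it is only tidying.

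The cost is SAP wording and one re-derived variable, using treatment dates and the missed-dose dates that SAP 11 says are in the eCRF. Reported compliance and the PP population may be slightly smaller. SAP 1 fixes population membership before unblinding, so the rule should be settled by then.
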